### **2.3.4 New Lesions**

The appearance of new malignant lesions alone does not denote disease progression. Instead, the diameter of new lesions is added to the sum of diameters for target and non-target lesions.

## **2.4 Evaluation of Best Overall Response**

The best overall response is the best response recorded from the start of the study treatment until the end of treatment taking into account any requirement for confirmation. The patient’s best overall response assignment will depend on the findings of both target and non-target disease.

### **2.4.1 Time Point Response**

It is assumed that at each protocol specified time point, a response assessment occurs. For patients experiencing irCR or irPR, a confirmatory scan obtained no less than 4 weeks after the

original scan is required to confirm the objective response. For patients experiencing irPD, but who demonstrate acceptable tolerability of treatment as evaluated by the Investigator, a confirmatory scan obtained no less than 4 weeks after the original scan is required for the confirmation of irPD.

**Immune-related response determination per irRECIST**

Target Lesions	Non-Target Lesions	%Change Tumor Burden	Immune-Related Response Status
CR	CR	-100%	irCR
PR	Any	≤-30%	irPR
PR	Any	≥-30% to <+20%	irSD
PR	Any	≥+20%	irPD
SD	Any	≥-30% to <+20%	irSD
SD	Any	≥+20%	irPD
PD	Any	≥+20%	irPD

No new lesions allowed to achieve irCR status. Otherwise, presence or absence of new measurable or new non-measurable lesions does not affect response status in isolation. New measurable lesions added to cumulative tumor burden to calculate % change tumor burden for the determination of immune-related response status.

**Immune-Related Complete Response (irCR):** Complete disappearance of all target and non-target lesions and no new lesions. The short axis of all lymph nodes must be ≤ 10 mm.

**Immune-Related Partial Response (irPR):** The sum of diameters has decreased ≥ 30% from the baseline but does not meet the criteria for irCR.

**Immune-Related Stable Disease (irSD):** The patient does not meet criteria for irCR, irPR or irPD.

**Immune-Related Progressive Disease (irPD):** The sum of diameters for target lesions and new measureable lesions has increased by ≥ 20% from the nadir sum of diameters.

**2.4.2 Missing Assessments and Inevaluable Designation**

When no imaging/measurement is done at all at a particular time point, the patient is not evaluable (NE) at that time point. If only a subset of lesion measurements is made at an assessment, usually the case is also considered NE at that time point, unless a convincing argument can be made that the contribution of the individual missing lesion(s) would not change the assigned time point response.

**2.4.3 Best Overall Response: All Time Points**

The *best overall response* is determined once all the data for the patient is known.

Complete or partial responses may be claimed only if the objective response is confirmed on a follow-up scan obtained no less than 4 weeks after the initial scan demonstrating an objective response. Absent this subsequent radiographic confirmation, irCR or irPR designations will be considered as unconfirmed responses.

## **2.4.4 Special Notes on Response Assessment**

When nodal disease is included in the sum of target lesions and the nodes decrease to ‘normal’ size (< 10 mm), they may still have a measurement reported on scans. This measurement should be recorded even though the nodes are normal in order not to overstate progression should it be based on increase in size of the nodes. As noted earlier, this means that patients with irCR may not have a total sum of ‘zero’ on the case report form (CRF).

Patients with a global deterioration of health status requiring discontinuation of treatment without objective evidence of disease progression at that time should be reported as ‘symptomatic deterioration’. Every effort should be made to document objective progression even after discontinuation of treatment. Symptomatic deterioration is *not* a descriptor of an objective response: it is a reason for stopping study therapy. The objective response status of such patients is to be determined by evaluation of target and non-target disease as shown in Table 1.

## **2.5 Confirmation/Duration of Response**

### **2.5.1 Confirmation**

Objective responses should be confirmed by CT and/or MRI scans obtained no less than 4 weeks after the original scan.

### **2.5.2 Duration of Overall Response**

The duration of overall response is measure from the time measurement criteria are first met for irCR/irPR (whichever is first recorded) until the first date that recurrent or progressive disease is objectively documented (taking as reference for progressive disease the smallest measurements recorded on study). The duration of overall complete response is measured from the time measurement criteria are first met for irCR until the first date that recurrent disease is objectively documented.

### **2.5.3 Duration of Stable Disease**

Stable disease is measured from the start of the treatment until the criteria for progression are met, taking as reference the *smallest sum on study* (if the baseline sum is the smallest, this is the reference for calculation of irPD).

1 INTRODUCTION

This study is an open-label, Phase 1b/2, dose escalation and cohort expansion study designed to characterize the safety, tolerability, pharmacokinetics (PK), pharmacodynamics, immunogenicity, and preliminary antitumor activity of MGD007 and MGA012, administered in combination by intravenous (IV) infusion, in patients with histologically proven, relapsed/refractory metastatic colorectal carcinoma.

This statistical analysis plan (SAP) describes in detail the statistical methods to be used for analysis of the primary and secondary efficacy endpoints, the safety endpoints, and the PK parameters to be collected from this study.

2 STUDY OBJECTIVES

2.1 Dose Escalation Phase

2.1.1 Primary Objectives

To characterize the safety, tolerability, dose-limiting toxicities (DLTs), and maximum tolerated dose (MTD) of MGD007 when combined with MGA012 in patients with relapsed/refractory metastatic colorectal carcinoma after at least 2 and up to 5 prior standard regimens of therapy in metastatic setting; or who did not tolerate fluoropyrimidines, oxaliplatin or irinotecan; or who are not good candidates for standard of care.

2.1.2 Secondary Objectives

- To characterize the pharmacokinetics (PK), pharmacodynamic activity, and immunogenicity of MGD007 and MGA012 in combination.
- To investigate the preliminary antitumor activity of MGD007 combined with MGA012 as measured by objective response rate, disease control rate, and progression-free survival (PFS) rate at 16 weeks in patients with relapsed/refractory metastatic colorectal carcinoma using both conventional Response Evaluation Criteria in Solid Tumors (RECIST 1.1) and immune-related response criteria (irRECIST).

2.1.3 Exploratory Objectives

- To explore the relationships between PK, pharmacodynamics of MGD007/MGA012, and antitumor activity.
- To explore the impact of this combination on PFS, immune-related PFS (irPFS), and overall survival (OS) in patients with relapsed/refractory metastatic colorectal carcinoma.
- To investigate the immunoregulatory activity of MGD007 combined with MGA012 in vivo, including various measures of T cell function in peripheral blood and/or tumor biopsy specimens.
- To assess potential biomarkers predictive of efficacy including but not limited to glycoprotein A33 (gpA33), CD3, TILs, PD-1, PD-L1, and immunosuppressive myeloid/lymphoid cells via immunohistochemistry and gene expression in archival tissue.

2.2 Cohort Expansion Phase

2.2.1 Primary Objective

To investigate antitumor activity of MGD007 combined with MGA012 when dosed at the MTD (or maximum administered dose [MAD] if no MTD is defined) as measured by objective response rate, disease control rate and PFS rate at 16 weeks in patients with relapsed/refractory metastatic colorectal carcinoma using both conventional Response Evaluation Criteria in Solid Tumors (RECIST 1.1) and immune-related response criteria (irRECIST).

2.2.2 Secondary Objectives

- To further characterize the safety and tolerability of MGD007 when combined with MGA012 in patients with relapsed/refractory metastatic colorectal carcinoma after at least 2 lines of therapy in a metastatic setting.
- To characterize the PK, pharmacodynamic activity, and immunogenicity of MGD007 and MGA012 in combination.
- To explore the impact of this combination on PFS, immune-related PFS (irPFS), and overall survival (OS) in patients with relapsed/refractory metastatic colorectal carcinoma.

2.2.3 Exploratory Objectives

[figure not shown]
- To explore the relationships between PK and pharmacodynamics of MGD007/MGA012 and antitumor activity.
- To investigate the immunoregulatory activity of MGD007 combined with MGA012 in vivo, including various measures of T cell function in peripheral blood and/or tumor biopsy specimens.
- To assess potential biomarkers predictive of efficacy including but not limited to glycoprotein A33 (gpA33), CD3, TILs, PD-1, PD-L1, and immunosuppressive myeloid/lymphoid cells via immunohistochemistry and gene expression in archival tissue and assess the effect of the combination on tumor biomarkers, comparing initial and on treatment paired tumor biopsies.

3 STUDY DESIGN AND PLAN

[figure not shown]
3.1 Overall Study Design and Plan

This study is an open-label, Phase 1b/2 dose escalation and cohort expansion study designed to characterize the safety, tolerability, PK, pharmacodynamics, immunogenicity, and preliminary antitumor activity of MGD007 and MGA012, administered in combination by IV infusion, in patients with histologically proven, relapsed/refractory metastatic colorectal carcinoma, irrespective of the KRAS and MMR status of their tumors. This study will enroll patients in 2 cohorts as described below.

QW Cohort: Overall Study Treatment Schema – MGD007 QW

Q2W Cohort: Overall Study Treatment Schema – MGD007 LID then Q2W

This study consists of two phases: a Dose Escalation Phase followed by a Cohort Expansion Phase. The Dose Escalation Phase will employ a 3+3+3 scheme to examine a series of increasing dose escalations in sequential cohorts of patients. Only the dose for MGD007 will be escalated; the dose for MGA012 will be kept constant at the dose of 3 mg/kg. For patients enrolled in QW cohort, 3 escalation doses of MGD007 (0.4, 0.6, and 0.8 $\mu\text{g}/\text{kg}$) are to be explored. For patients enrolled in Q2W cohort, 3 escalation doses of MGD007 (0.5, 0.8, and 1 $\mu\text{g}/\text{kg}$) are to be explored along with LID dose of 0.5 $\mu\text{g}/\text{kg}$. MGD007 will be given as 120-minute infusion and MGA012 IV will be given as 60-minute infusion. On days when both MGD007 and MGA012 will be administered, MGA012 will be administered first.

Intermediate dose levels may be explored selectively during the dose escalation portion of the study. Any escalation cohort, not exceeding the MTD, can be expanded to a maximum of 15 patients for further evaluation of safety and efficacy.

DLTs will be based on the occurrence of drug-related AEs that occur up to Cycle 1 Day 42 in both the QW and Q2W Cohort.

The Cohort Expansion Phase will include 25 patients in each of the 2 treatment cohorts to further define the safety and initial antitumor activity of the combination with the doses established in the Dose Escalation Phase; approximately 90% of these will be MSS patients and 10% MSI-H.

A full description of the study evaluations, including the number and timing of visits and the procedures to be performed at each visit can be found in Appendices 1 and 2 (Time and Events Schedule) of the protocol.

3.2 Sample Size

The study plans to treat approximately 104 patients: up to 27 in each of two treatment cohorts in Dose Escalation Phase and approximately 25 in the Cohort Expansion Phase in each of the two treatment cohorts.

The sample size of up to 27 patients for each cohort in the Dose Escalation Phase is based on 3+3+3 design with planned 3 dose cohorts. Additional patients may be enrolled to replace non-evaluable patients or if the enrollment to a dose cohort is expanded (up to 15 patients) or intermediate dose levels are evaluated in Dose Escalation Phase.

The Cohort Expansion Phase plans to treat approximately 25 patients in relapsed/refractory metastatic colorectal carcinoma in each cohort, approximately 90% of them are MSS patients, e.g., 22 MSS and 3 MSI-H patients. At the end of the Cohort Expansion Phase, 15 paired tumor biopsies will be required in each cohort, if tumor lesions are accessible with acceptable clinical risk. If 15 paired biopsies have not been collected in the initial 25 patients, additional patients with paired tumor biopsies will be enrolled, to ensure that the 15 paired biopsies are obtained.

The sample size in the Cohort Expansion Phase is primarily based on providing preliminary estimation of objective response rate and disease control rate. [Table 1](#) provides the 2-sided 95% confidence interval (CI) for a number of potential responses among 25 patients in each cohort.

Table 1 **Response Rates and 95% Confidence Intervals**

Sample Size	Number of Responses	Response Rate (%)	95% Confidence Interval (%)
25	2	8	1.0, 26.0
25	3	12	2.5, 31.2
25	4	16	4.5, 36.1
25	5	20	6.8, 40.7
25	6	24	9.4, 45.1
25	7	28	12.1, 49.4

During the Cohort Expansion Phase, patients who withdraw before completing the first tumor assessment for a reason other than clinically confirmed progressive disease or death is considered unevaluable for response. In these cases, replacement patients may be enrolled in the same dose level.

4 ANALYSIS POPULATIONS

4.1 Analysis Populations

The study analyses will be performed on the following populations:

- **Safety Population:** All patients who received at least one dose of any study drug. This population will be used for analyses of safety, PD, and immunogenicity. It will also be used for summary of baseline data and analyses of PFS and OS.
- **Response Evaluable Population:** All patients who received at least one dose of any study drug, had baseline measurable disease, and had at least one post-baseline radiographic tumor assessment or discontinued treatment due to clearly documented, clinically progressive disease or death. This population will be used for summary of tumor assessment data and analyses of response rates.

5 ENDPOINTS

5.1 Efficacy Endpoints

5.1.1 Response Endpoints

- Response by RECIST v1.1: The best overall response (BOR) will be categorized as CR, PR, SD, PD, or NE. To be qualified as BOR, CR and PR require confirmation at least 4 weeks after initial observation of such response, and SD requires to be observed at least once after 8 weeks (minus 3 days) from the start of MGD007 treatment.
- Immune related Response by irRECIST: The best overall response (BOR) will be categorized as irCR, irPR, irSD, irPD, or irNE. To be qualified as BOR, irCR, irPR, and irPD require confirmation at least 4 weeks after initial observation of such response, and irSD requires to be observed at least once after 8 weeks (minus 3 days) from the start of MGD007 treatment.

5.1.2 Time to Event Endpoints

- Progression-free survival (PFS): The PFS is defined as the time from the first dose date of MGD007 to the date of first documented progression or death from any cause, whichever occurs first. For patients who are not known to be dead or progressed at the time of data cut-off for PFS analysis, the PFS will be censored at the date of the last tumor assessment. The documented progression is determined by radiographic assessment using RECIST v1.1. PFS will be calculated as:

$$\text{PFS (months)} = (\text{date of event [documented progression or death] or date of censoring} - \text{first dose date} + 1) / (365.25/12)$$

- Immune related PFS (irPFS): The irPFS is defined as the time from the first dose date of MGD007 to the date of first documented immune related progression (irPD) or death from any cause, whichever occurs first. For patients who are not known to be dead or progressed at the time of data cut-off for irPFS analysis, the irPFS will be censored at the date of the last tumor assessment. The documented irPD is determined by radiographic assessment using irRECIST. The irPFS will be calculated as:

$$\text{irPFS (months)} = (\text{date of event [documented immune related progression or death] or date of censoring} - \text{first dose date} + 1) / (365.25/12)$$

- Duration of response (DoR): The DoR is defined as the time from the date of initial response (CR or PR) to the date of first documented progression or death from any cause, whichever occurs first. The DoR is calculated only for the responders. For responders who are not known to be dead or progressed at the time of data cut-off for DoR analysis, the DoR will be censored at the date of the last tumor assessment. The documented progression is determined by radiographic assessment using RECIST v1.1. DoR will be calculated as:

$$\text{DoR (months)} = (\text{date of event [documented progression or death] or date of censoring} - \text{date of initial response} + 1) / (365.25/12)$$

DoR may also be determined by irRECIST.

- Overall survival (OS): The OS is defined as the time from the first dose date of MGD007 to the date of death from any cause. For patients who are not known to be dead at the time of data cut-off for OS analysis, the OS will be censored at the time they are last known to be alive. OS will be calculated as:

$$\text{OS (months)} = (\text{date of death or last known alive} - \text{first dose date} + 1) / (365.25/12)$$

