## 9.11 End of Treatment Visit

A list of evaluations to be performed for the EOTV is provided in [Appendix 1](#); a CT or MRI Scan should be performed during the EOTV, unless a previous scan was performed < 28 days of the EOTV. Criteria for triggering the End of Treatment visit are specified in [Section 5.4](#).

The End of Treatment Visit should be performed after the patient has met off-study criteria. This visit should occur no later than 30 days since the last study dose and before any subsequent anti-cancer treatment. If EOTV < 30 days since the last study dose, the site should contact the patient for safety follow-up no later than 30 days after the last study dose (see [Section 12](#)). It is recognized that certain patients (such as those experiencing progression of disease) may be cared for in facilities other than the participating study site, may proceed to receive other cancer therapy, and/or may elect not to return to the study site. Therefore, this visit is considered optional, but should be carried out whenever possible. All required procedures and tests should be performed if a visit is performed.

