### 14.6.3 Time-to-event Endpoints and Analyses

Progression-free survival will be defined as the time from the first dose date of MGD007 to the date of first documented progression or death from any cause, whichever occurs first. The documented progression is determined by objective assessment of disease per RECIST v1.1 and irRECIST, respectively. For patients who are not known to be dead or progressed at the time of data cut-off for PFS analysis, the PFS will be censored at the date of the last tumor assessment. Specifically, the following censoring rules will be applied as primary analysis of PFS. Sensitivity analyses may be performed to assess the robustness of the primary PFS analysis and will be described in the SAP.

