6.6 Efficacy Endpoint Analyses

6.6.1 Analyses of Response Endpoints

Number and percent of patients with their best overall response will be summarized. The objective response rate (ORR) per RECIST v1.1 is estimated as the proportion of patients in response evaluable population who achieve BOR of CR or PR. Disease control rate is calculated as the proportion of patients who achieve a CR, PR, or SD. Progression-free survival rate at 16 weeks will be calculated by Kaplan-Meier method described in [Section 6.6.2.1](#), based on response evaluable population and safety population, respectively. The 2-sided 95% exact binomial CI of the response rates will be calculated. The response rates per irRECIST will be estimated similarly. Subgroup analyses of these response rates by KRAS gene type (wild and mutant) and by MMR status (MSS and MSI-H) will be performed.

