6.6.2 Analyses of Time to Event Endpoints

6.6.2.1 PFS and irPFS

The Kaplan-Meier method will be applied to estimate PFS curve, median PFS, and PFS rates at 4 (corresponding to 16 weeks), 6, and 12 months. The method of Brookmeyer and Crowley (1) will be used to construct 95% CI for median PFS. The 95% CIs for PFS rate at 4, 6, and 12 months will be calculated by normal approximation after log(-log) transformation.

For primary PFS analysis, the following table describes the censoring rules.

Table 2 Censoring Rules for Primary PFS Analysis

Situation	Date	Outcome
No baseline tumor assessments	First dose date	Censored
Death prior to first scheduled tumor assessment	Date of death	Progressed
No post-baseline tumor assessments in absence of death prior to first scheduled tumor assessment	First dose date	Censored
Documented progression	Date of progression	Progressed
Initiation of alternative anti-cancer treatments in absence of documented progression	Date of last tumor assessment prior to initiation of such treatment	Censored
Death or documented progression immediately after missing two or more consecutive scheduled tumor assessments	Date of last tumor assessment prior to missed assessments	Censored

PFS will be analyzed by MMR status and by KRAS gene type when sample size warrants. A sensitivity analyses for PFS may be performed to assess the robustness of above primary PFS analysis. For this sensitivity analysis, the censoring rules are the same as in **Table 2** except that the documented progression or death will be considered as an event, regardless of when it occurs during the study.

In addition, above analyses for PFS will also be repeated for irPFS.

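### Living patients who stop for documented clinical progression with no post-baseline scan are failures in ORR and DCR but are censored at first dose in the 16-week PFS rate, and no planned sensitivity analysis counts clinical progression as an event

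*SAP*

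**What the plan says.** **Event.** SAP 5.1.2 states: "The documented progression is determined by radiographic assessment using RECIST v1.1". Protocol 14.6.3 agrees: "The documented progression is determined by objective assessment of disease per RECIST v1.1 and irRECIST, respectively". For patients not known to have died or progressed, "the PFS will be censored at the date of the last tumor assessment".

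**Censoring table.** SAP 6.6.2.1, Table 2 (the same as Protocol Table 14) has two rows that matter for a treated patient with a baseline scan and none afterwards. "Death prior to first scheduled tumor assessment" is an event at the date of death. "No post-baseline tumor assessments in absence of death prior to first scheduled tumor assessment" is censored at the first dose date. No row covers clinical progression. The same analyses are repeated for irPFS.

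**Populations.** Under SAP 4.1, a Response Evaluable patient must, among other conditions, have "had at least one post-baseline radiographic tumor assessment or discontinued treatment due to clearly documented, clinically progressive disease or death". ORR uses this population (SAP 6.6.1). DCR needs CR, PR or SD, and SAP 5.1.1 requires SD to be seen at 8 weeks (minus 3 days) or later. The 16-week PFS rate is a Kaplan-Meier estimate "based on response evaluable population and safety population, respectively".

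**Sensitivity analysis.** SAP 6.6.2.1 allows, but does not require, one further PFS analysis. It counts documented progression or death as an event whenever it occurs, and otherwise keeps Table 2.

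**End-of-treatment scan.** Protocol 9.11 plans a scan at the End of Treatment Visit unless one was done less than 28 days before. It then recognizes that some patients, including some with progression, may not return: "Therefore, this visit is considered optional, but should be carried out whenever possible".

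**The concern.** Kaplan-Meier assumes that a censored patient has the same future risk as those still followed. A patient taken off treatment because the disease has clearly worsened does not. Censoring at first dose removes that patient from every risk set, so a known early failure contributes nothing to the 16-week PFS rate.

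The plan already recognizes such patients as failures. The population definition keeps them in the denominator for response, and without a scan they cannot have CR, PR or SD. Two of the three measures in the expansion phase's primary objective therefore count the patient as a failure, and the third leaves the patient out. In a single-arm study the absolute rate is the result, and its confidence interval does not reflect a bias of this kind.

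**Working it through.** **Inputs.** Expansion N = 25 (Protocol 14.1). First scan at Day 56 (±3 days), then every 8 weeks, so week 16 is Day 112. The documents do not give the number of living clinical progressors with no post-baseline scan, k, or the true 16-week PFS rate, so both are assumed.

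- *True rate.* The central assumption is 20%, or x = 5 of 25. For orientation, Protocol 2.1 cites 20-week immune-related PFS for another anti-PD-1 antibody: 2 of 18 in MMR-proficient and 7 of 9 in MMR-deficient CRC. For the planned 22 MSS and 3 MSI-H patients, (22 × 2/18 + 3 × 7/9)/25 = 19.1%.
- *k.* The nearest proxy is the monotherapy study (Protocol 2.3.4, Table 2), where 8 of 59 patients were not evaluable; 25 × 8/59 = 3.4. It is imperfect because the reasons are not given. The range used is 0 to 5.

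**Step 1: the plan's own figures.** Exact binomial intervals for 2 to 7 responses in 25 reproduce all six rows of SAP Table 1 (for example 5/25: 6.8 to 40.7%). The plan states no precision for the 16-week PFS rate.

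**Step 2: patients with no scan.** With no other censoring, censoring k patients at first dose gives x/(25−k). Counting them as events gives x/25. The ratio is 25/(25−k). For x = 5:

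| k | Table 2 rule | Clinical progression as event | Ratio |
|---|---|---|---|
| 0 | 5/25 = 20.0% | 20.0% | 1.00 |
| 1 | 5/24 = 20.8% | 20.0% | 1.04 |
| 2 | 5/23 = 21.7% | 20.0% | 1.09 |
| 3 | 5/22 = 22.7% | 20.0% | 1.14 |
| 5 | 5/20 = 25.0% | 20.0% | 1.25 |

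The log(−log) 95% interval is 7.3 to 37.2% for 5/25 and 8.3 to 41.4% for 5/22. For true rates of 12%, 20%, 28% and 40%, the upward bias is 1.6, 2.7, 3.8 and 5.5 points at k = 3, and 3.0, 5.0, 7.0 and 10.0 points at k = 5.

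**Step 3: patients who progress clinically after a Day 56 scan without PD.** Their scan meets the SD rule, so they count as disease control and DCR does not contradict PFS. They are censored at Day 56. The example needs an assumed split of the other events:

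- Three such patients, 11 events at Day 56 and 6 at Day 112: (14/25) × (5/11) = 25.5%.
- Five such patients, 10 events at Day 56 and 5 at Day 112: (15/25) × (5/10) = 30.0%.

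Both compare with 20.0% when clinical progression is an event. This is informative censoring at the last scan, a separate problem from Step 2.

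**Step 4: do the other provisions close the gap?**

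- *Safety Population version.* The clinical progressors with no scan are in both populations, and Table 2 treats them the same way in both.
- *Sensitivity analysis.* It reaches a clinical progressor who dies or has scan-documented PD by week 16. It misses one who is alive without documented PD at week 16; if that patient dies later, the event falls after the time point.
- *Follow-up.* Response status is sought every 3 months in some patients who stop treatment (Protocol 9.12 and 11.1.1), but no scan is mandated.

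**The case against.** Radiographic-only PFS is a deliberate and consistent choice. Protocol 14.6.3 requires objective assessment, and Appendix 5 treats symptomatic deterioration as a reason for stopping therapy, not as an objective response category. In an open-label single-arm study, letting investigator judgement end PFS adds subjectivity. This stands, and it is why the primary definition should not change. A reader might infer that the definition itself is an error; the documents do not support that.

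Mitigation exists. A scan is planned at the End of Treatment Visit, which is to take place whenever possible, and Appendix 5 asks for every effort to document objective progression after stopping. These provisions lower k, and a scan showing PD makes the patient an event. A reader might also take Protocol 9.11 to expect progressing patients to skip the scan, but it only recognizes that some may not return. What remains is that no scan is guaranteed.

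The consequence is limited. The SAP is mainly descriptive, the expansion size was set for ORR and DCR, and no threshold or test rests on 16-week PFS. This also stands.

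Finally, a reader might infer that every clinical progressor is handled in opposite ways by DCR and PFS, and pool both groups to get a large inflation. Take 2 patients with no scan, 11 events at Day 56, 3 patients censored at Day 56, and 4 events at Day 112. The rate is (12/23) × (5/9) = 29.0% against 20.0%. Counting only the two no-scan patients as events still gives (12/25) × (5/9) = 26.7%, so most of the excess comes from the three patients who keep SD. The contradiction with DCR is confined to those with no scan.

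**Conclusion.** The point holds for living patients who stop for documented clinical progression with no post-baseline scan. ORR and DCR count them as failures, and Table 2 censors them at first dose in a measure of the same primary objective. The 16-week PFS rate is then too high by a factor of 25/(25−k) if there is no other censoring. At k = 3 and an assumed true rate of 20% that is 2.7 points, against an interval of 37.2 − 7.3 = 29.9 points. The direction follows from the plan's rules; the size rests on assumed values of k and the true rate.

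For patients who progress clinically after a qualifying scan, the only problem is informative censoring at that scan. The optional sensitivity analysis helps with those who die or have documented PD by week 16, so it would be wrong to say it does nothing, but it leaves the central group uncounted. This is a moderate weakness that a prespecified analysis can expose. It does not invalidate the PFS definition.

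**What to change.** Keep radiographic PFS as the primary definition. In SAP 6.6.2.1, prespecify a mandatory sensitivity analysis of the 16-week PFS and irPFS rates in which stopping treatment for clearly documented clinical progression, without radiographic PD, is an event at the discontinuation date. For these patients the rule should take precedence over the no-scan row of Table 2. Report the result beside the radiographic-only rate, with the number of patients reclassified, split into those with no post-baseline scan and those with an earlier scan.

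The cost is SAP wording and one extra Kaplan-Meier run per criterion. No new data should be needed: the Response Evaluable definition already requires these patients to be identified, and SAP 6.3.1 already tabulates reasons for discontinuation. The drawbacks are some investigator subjectivity in the sensitivity result and a rate that may be lower than the radiographic one.
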